### **Retrospective Arm**

The following baseline and procedural data points will be summarised for both the retrospective and the prospective arms. Although the study is not powered to make comparisons between the retrospective surgical patients and the prospective Urolift subjects, comparisons in the observed data will be made statistically. Continuous variables will be compared using a t-test or non-parametric alternative, binary data points will be compared using chi-square or Fisher's exact test.

- 1) Baseline demographics

- 2) Duration of catheterisation to procedure (days)
- 3) Procedure time
- 4) Hospitalisation time

The following outcomes post procedure will be summarised for the retrospective surgical group and will compared to the results obtained in the prospective study. The statistical significance of any observed differences will be assessed.

- 1) Total numbers of related AE, SAE, and Clavien-Dindo  $\geq$ IIb individually
- 2) Percent procedure/device related AE rates by month post index procedure and by severity
- 3) Retreatment post index intervention by time to event and by month
- 4) Medical treatment post index intervention by time to event and by month
- 5) Urinary retention recurrence rates at 1 month, 6 weeks and at 3, 6 and 12 months
- 6) Post-procedure TWOC success percent
- 7) Catheterisation use

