## 6.4 Other Assessments

---

Several other outcomes will be analyzed during the 12 month follow-up to understand post-TWOC durability:

- Catheter free rate and days free from catheter at 1 month and throughout follow-up
- Number of subjects who failed initial attempt but are able to void in subsequent TWOC
- Need for further clean intermittent self-catheterisation (CISC)
- Urinary symptoms peak flow rate, post void residual (PVR) volume
- Subjects free from alternative surgical procedure for BPH
- Duration of pre-index procedure catheter and its impact on durability
- Rate of adverse events
- The prospective arm will be compared to the available data collected in the retrospective surgical arm

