### 13.2 Anticipated Adverse Events

---

Adverse events will be solicited from the subject and documented after enrolment (see section 14 Adverse Events) the UroLift System Treatment, and at each follow-up time point. The risks of the undergoing the PUL procedure as part of this study are the same as having the procedure without being in the study.

Possible anticipated adverse events may be, but are not limited to those symptoms or events related to the disease process, the procedure (Section 13.3), device use (Section 13.5), reactions to medication inclusive of anaesthesia, and/or the study testing.

Anticipated adverse events that are: (1) reflective of the disease process (such as exacerbation of LUTS) and/or (2) inherent to this and any prostatic invasive procedure and expected to occur in this subject population are still to be reported as AEs during this study.

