### 13.3 Anticipated Procedural Adverse Events

---

Possible anticipated complications related to procedure, anaesthesia and medication include, but are not limited to: death, damage to non-urinary systems, surgical trauma, bleeding, catheter misplacement, allergic reaction, decrease in kidney function, pulmonary embolism and infection.

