## 14.5 Adverse Event Reporting

Adverse events will be collected on all enroled subjects. Subjects will be asked about adverse events at each visit, and all AEs will be documented and reported regardless of relatedness.

Adverse events will be documented on the AE electronic case report form (eCRF) within the study's Electronic Data Capture System (EDC).

When an SAE occurs, the Sponsor should be notified within 24 hours of site awareness via completion of the AE eCRF in the EDC System. Sponsor will receive an alert upon any SAE entry and will be responsible for reporting to notified body, ethics committee and all other participating investigators as applicable. Should Sponsor determine, either through investigator reports or in-house testing, that a unexpected SAE presents an unreasonable risk to all participating subjects, Sponsor will suspend the clinical investigation.

It is the responsibility of the Chief Principal Investigator to report all related and unexpected Serious Adverse Events (SAEs) to the ethics committee. The Sponsor may report on behalf of the Chief Investigator. Device-related SAEs in this study, using a CE-marked device in a post-market surveillance study, are reportable to the MHRA Adverse Incident Centre as reported under the requirements of the Devices Vigilance requirement.

Annual and final reports will be provided to the EC as applicable per EC requirements with Sponsor assistance.

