### 15.8.2 Procedure

The following will be collected (if available):

• Date, duration	• Type of facility, type of surgery	• Complications, adverse events (urological, sexual function, cancer and SAEs)	• Duration of hospital stay
• Catheterisation	• Pathology (documentation only)		

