### 15.8.3 Post-procedure

The following post-surgery data will be collected for period after discharge through 12 months after their surgical intervention (if available):

• Date of contacts	• Type, reason of contact (phone, office visit)	• Complications, adverse events (urological, sexual function, cancer and SAEs)	• Interventions
• BPH medications, indication	• Symptom scores	• Uroflowmetry/PVR	• Catheterisations

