		
 
2. Removed questionnaire and UA requirements at post-procedure.
 
3. SHIM only required at baseline and follow-up if subject is sexually active.
 
4. Defined treatment failure, alternative procedure and secondary PUL criteria.
 
5. Urine cultures only required if UA is abnormal, CS and indicates a urinary infection. Required uploads for abnormal UAs and urine cultures.
 
6. Removed 125ml minimum voided volume for uroflows at follow-up.
 
7. Removed requirement to discontinue alpha blockers on day of index procedure.
 
8. Removed requirement for ultrasound uploads.
 
9. Revised require case requirements for PIs from 50 to 30.
 
10. Expanded re-catheter rate assessment to 1 month. Added re-catheter assessment to secondary assessments and removed from primary study assessment.
 
11. Only AEs related to cancer, LUTs, SAEs and sexual function are required to be collected in the Retrospective arm.
 
12. Revised 4 centres to 6 centres
 
13. removed the word transrectal to include ultrasound as a method to evaluate prostate size.
 
14. Defined symptoms not considered an adverse event.
 
15. Minor risk revisions
 

D	14 Dec 2018	
 
1. Admin change on Protocol Signature Page: removed duplicate Sponsor signature
 
2. Admin change on Table 7: removed Urine C&S "if indicated" at 6 months. This was a typo. A UA is not required.
 
3. Increased sample size to up to 55 subjects
 

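### The between-arm comparison of related adverse events in 16.6 is not confined to events captured and counted alike in both arms, and its Clavien-Dindo cut of ≥IIb is not a grade in Table 10

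*Combined protocol and SAP*

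**What the plan says.** **The comparison.** Section 16.6, Retrospective Arm, lists the post-procedure outcomes to be compared, with the significance of differences assessed. Item 1 is "Total numbers of related AE, SAE, and Clavien-Dindo" ≥IIb, each individually. Item 2 is procedure- or device-related AE rates by month and severity. Neither names an event class. Section 6.4 adds: "The prospective arm will be compared to the available data collected in the retrospective surgical arm".

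**Capture in the PUL arm.** Section 13.2: "Adverse events will be solicited from the subject and documented after enrolment". Section 14.5: "all AEs will be documented and reported regardless of relatedness".

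**Capture in the surgical arm.** Section 15.8.2 opens with "The following will be collected (if available"), and both it and 15.8.3 list "Complications, adverse events (urological, sexual function, cancer and SAEs"). The entry for revision C in the revision history points the same way: "Only AEs related to cancer, LUTs, SAEs and sexual function are required to be collected in the Retrospective arm".

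**Counting rules.** Section 14.3 says that recurrent urinary retention (other than clot retention), clinically insignificant colonisation in men needing a catheter, and the need for an alternative procedure are not AEs. Section 10.10.1 limits reporting after alternative surgery to urological SAEs. Section 16.3 censors safety data on the day of that surgery. Section 15 contains no counterpart to these rules for the surgical charts.

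**Grading.** Section 14.6 has the independent reviewer grade events with onset within 90 days of the index procedure by Clavien-Dindo, using Table 10.

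**The concern.** A comparison of related AEs is interpretable only if the same kinds of event can enter the count in both arms under the same rules. Here the PUL count is open to all classes while the surgical count appears limited to four, and the rules for what counts as an AE are written for the PUL arm only. In addition, a threshold that is absent from the grading table cannot be programmed. Someone must choose what it means, possibly with the data in view.

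The AE comparison is additional assessment 6 in the Protocol Summary and serves the objective in 6.1 of comparing benefits and risks with surgery. An unequal count could therefore colour the descriptive picture that is carried into the larger randomised study.

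**Working it through.** There is no figure in the plan to reproduce: no power, alpha or surgical sample size is given for this comparison. The check is mainly a comparison of sections.

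**1. Event class.** The PUL arm takes all classes (13.2, 14.5). The surgical arm takes complications, plus AEs that are urological, sexual, cancer-related or serious (15.8.2, 15.8.3).
- If the bracket governs both nouns, non-serious related events outside the four classes enter only the PUL count. Section 13.3 anticipates some such events: "damage to non-urinary systems, surgical trauma, bleeding, catheter misplacement, allergic reaction". Some of these would be urological or serious and so shared; a mild allergic reaction would not.
- In 13.5, about 5 of 38 listed entries fall outside the shared classes unless serious: allergic or tissue reaction, embolisation, gastrointestinal changes, hypo- or hypertension, and pyrexia. These are lines in a list, not event rates.
- If complications is unrestricted, this mismatch largely disappears.

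Section 6.4 limits the surgical side to what is available but does not filter the PUL side.

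**2. Counting rules within the shared classes.**

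| Event | PUL arm | Surgical arm |
|---|---|---|
| Recurrent retention | Not an AE (14.3) | No rule in section 15; could be abstracted as a urological complication |
| Insignificant colonisation | Not an AE (14.3) | No rule |
| Need for an alternative procedure | Not an AE (14.3) | No rule |
| Events after surgical retreatment | Urological SAEs only (10.10.1); censored (16.3) | Collected to 12 months (15.8.3); no censoring rule |

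Where abstractors do not apply the PUL rules, these rows add events to the surgical count only. They pull in the opposite direction to step 1.

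**3. The grade.** Table 10 defines I, II, III, IIIa, IIIb, IV, IVa, IVb and V: nine labels, with grade II undivided. The candidate readings count different events:
- ≥II includes complications needing drug treatment or transfusion.
- ≥IIIa starts at a surgical, endoscopic or radiological intervention.
- ≥IIIb starts at an intervention under general anaesthesia.

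**4. Illustration of step 1 alone.** Every input except the 55 PUL men is an assumption: 30% of men in each arm with a related AE in a shared class, 30 or 55 surgical men, and a share d of PUL men whose only related AE lies outside the shared classes. With A ~ Bin(55, 0.30 + d) and B ~ Bin(n, 0.30), the probability sums over all tables with exact two-sided Fisher p < 0.05 and a higher PUL proportion.

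| d | n = 30: against PUL (either direction) | n = 55: against PUL (either direction) |
|---|---|---|
| 0 | 1.7% (3.7%) | 1.6% (3.1%) |
| 2% | 2.7% (3.9%) | 2.7% (3.6%) |
| 5% | 4.8% (5.4%) | 5.6% (5.9%) |
| 10% | 11.4% (11.6%) | 14.7% (14.8%) |

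Class mismatch alone changes little until d nears 10%, and nothing in the documents supports a value that high. Chart under-capture is a separate matter that a class filter does not cure. With shared classes only and 75% of surgical events found in the charts (0.30 × 0.75 = 0.225 against 0.30), the chance of a significant result against PUL is 8.3% (n = 30) or 10.1% (n = 55). The model is one test on men with at least one event. The plan's outputs are totals and rates by month and severity, so these figures show sensitivity only.

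**The case against.** The strongest reply is that the mismatch in step 1 is conditional. Related events in a surgical chart are largely complications, and that word stands before the bracket. Table 12 says that all data will be abstracted (in its row on blinding) and that variables are used for consistency between arms. Section 15 describes a comparison on specific outcomes. The revision history says what is required, which may be only a minimum, and it is a log rather than the operative text. Section 16.6 presents AEs by system organ class and preferred term, so out-of-class PUL events would be visible. All of this stands as a reason for caution. None of it says that the PUL count will be filtered or that complications are unrestricted, so a clarifying sentence is still needed.

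On the grade, the likeliest explanation is a dropped character, and an error in the text extraction cannot be fully excluded. That makes it a one-label correction, but the intended label still has to be stated.

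A reader might infer that the comparison as a whole is biased against PUL. The documents do not support this: only the class mismatch and chart under-capture act in that direction, while the rules in 14.3 could favour PUL. A reader might also infer that SAEs and the shared classes are already like for like. Step 2 shows that they need not be. Finally, one might object that totals will be compared across arms of unequal size. Additional assessment 6 in the Protocol Summary refers to a rate, and 16.6 names chi-square or Fisher tests for binary data, so denominators are largely implied.

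**Conclusion.** The point holds and is minor. As written, items 1 and 2 of 16.6 can set a PUL count open to all event classes against a narrower surgical count, under AE definitions and censoring stated for PUL only. The effect of class mismatch is probably small, and it depends on how complications in 15.8 is read. The net direction of bias across all the differences is unknown. The probabilities shown above rest on assumed rates and must not be quoted as the size of the bias.

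The ≥IIb threshold cannot be applied with Table 10 in the supplied text. That conclusion needs no assumption beyond the accuracy of the extracted symbol.

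A reader might conclude that this undermines the study's findings. It does not: 16.6 states that the comparison is unpowered, 16.7 sets no success criterion, and the single-arm safety summary is unaffected.

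**What to change.** In 16.6:

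(a) Restrict the between-arm comparison in items 1 and 2 to urological, sexual function, cancer and serious events in both arms. In that comparison, apply the same 14.3 counting exclusions and the same censoring at surgical retreatment to both arms. Keep the full PUL AE listing as a single-arm table, and state that under-ascertainment from charts remains. If complications in 15.8 is meant to be unrestricted, say so and drop the class filter for complications.

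(b) Before looking at the data, replace ≥IIb with a grade that exists in Table 10, or tabulate each grade (II, IIIa, IIIb, IV, V). Use events with onset within 90 days of the index procedure in both arms; 15.3.1 already calls the invasive surgery the index procedure. Tabulating by grade covers every candidate reading, whereas showing only ≥II and ≥III would miss ≥IIIb.

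Cost: wording in 16.6 and a filter on data already planned. Section 15.8.3 already collects interventions and catheterisations, and 16.6 already needs retreatment, retention recurrence, relatedness and Clavien-Dindo grades for the surgical arm, so no visits or abstraction fields are added. Judging whether charted colonisation was clinically significant is a small extra review task. The downside is fewer event types in the comparative table.

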## 7 Study Design

---

The study is a multi-centre, consecutive, prospective feasibility study of the UroLift System in acute urinary retention (AR) patients. A retrospective dataset (patients treated from June 1, 2015 to December 31, 2015) of patients meeting similar criteria that underwent an invasive procedure to treat AR will be analysed against UroLift data. A maximum of 55 subjects undergoing UroLift will be enroled in up to six study centres in Great Britain. This feasibility study is the first to assess patients undergoing PUL with AR and will determine if a larger, quantitative study should be conducted with optimal methodology. By evaluating results pertaining to study design, primary study assessment, conduct of trial, site performance, subject compliance, and inclusion criteria specifically, a robust safety and effectiveness study can follow.

Clinical improvements will be assessed at post-procedure, 6 weeks, and months 3, 6, and 12 post-index procedure.

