#### 14.4 Adverse Event Assessment

Any AE experienced after the first UroLift device is introduced (enrolment) will require reporting on the eCRF. In general, a primary diagnosis for the event should be reported instead of each symptom, with the exception of LUTS. Lower urinary tract symptoms should be reported individually per the elements of IPSS. Only exacerbated conditions or new onset qualify as an AE, but if patient history is in question, report AE conservatively.

Adverse events will be summarised by overall adverse events (AEs), severe AEs (grade 3 or higher on CTCAE scale (See **Table 11**), AEs related to device and/or procedure (See **Table 9**), serious adverse events (SAEs) and SAEs related to device and/or procedure. Adverse events will be coded using MedDRA and Common Terminology Criteria for Adverse Events (CTCAE) severity grades and will be presented by System Organ Class (SOC) and preferred term.

Principal Investigators will be responsible for assessing severity via the CTCAE scale (**Table 11**) and Relatedness (**Table 9**).

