## 14.6 Adverse Event Independent Reviewer

---

An independent reviewer will be employed for safety review. The independent reviewer will provide comprehensive medical review and adjudicate the reported adverse events. The assessments of the independent reviewer will help to ensure that the adverse event data is accurate, free of bias, and consistently reported across the participating study centres. This independent reviewer will be an independent urologist, with no ties to Sponsor or any of the participating ECs or third party providers. A Safety Plan that describes the adjudication conventions will be established. The independent reviewer will review events, with the support of redacted source documents, to determine AE/SAE/UAE classification, event relatedness, degree of relatedness, event severity, and MedDRA coding. Adjudication will occur ongoing throughout the study and to be completed in advance of the study final report.

Adverse Events with onset within 90 days of Index Procedure will be evaluated by independent reviewer per the Clavien-Dindo (CD) classification (**Table 10**).

The independent reviewer may also categorize by CTCAE classification (**Table 11**). Complications, outside the recovery course, will be assigned a CD grade.

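### Section 16.6 tests adverse event totals between UroLift and retrospective surgery without a denominator, common window, common counting rule or common AE scope

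*Combined protocol and SAP*

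**What the plan says.** - **What is compared.** In section 16.6, Retrospective Arm, item 1 of the post-procedure list is "Total numbers of related AE, SAE, and Clavien-Dindo" at grade IIb or above as printed, each taken individually. The list is introduced with "The statistical significance of any observed differences will be assessed". Item 1 has no denominator, time window or method for counts. The only tests named are in the preceding paragraph on baseline and procedural data: a t-test or non-parametric alternative for continuous variables, and "binary data points will be compared using chi-square or Fisher's exact test". That paragraph also concedes that "the study is not powered to make comparisons between the retrospective surgical patients and the prospective Urolift subjects". Item 2 adds percentages of related AEs by month and severity.
- **Arm sizes.** Section 7: "A maximum of 55 subjects undergoing UroLift will be enroled". The surgical arm (sections 15 and 15.2) is every eligible, consenting case operated on from June to December 2015. No number is given.
- **Counting rule.** Section 14.4 is framed around events after the first UroLift device is introduced. It wants one primary diagnosis per event, with LUTS as the exception: "Lower urinary tract symptoms should be reported individually per the elements of IPSS". Section 15 gives chart abstractors no corresponding rule.
- **AE scope.** Under section 14.5, subjects are asked about AEs at each visit and every AE is recorded. Sections 15.8.2 and 15.8.3 limit surgical AEs to urological, sexual function and cancer events and SAEs, where the chart has them.
- **Grading.** Section 14.6: "Adverse Events with onset within 90 days of Index Procedure will be evaluated by independent reviewer per the Clavien-Dindo (CD) classification". Table 10 sets sequelae aside and subdivides only grades III and IV.

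**The concern.** A total of events is not a measure of risk until it is divided by men or person-time, and its variance depends on how events cluster within men. Here the denominators are unequal and one is unknown, and the rules that turn a clinical course into a number of AEs are written for one arm only. A significant difference between totals could come from arm size, from one man's symptoms being entered as several AEs, or from direct questioning being set against chart review.

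This matters because section 6.1 makes the comparison of benefits and risks with surgery a study objective, and section 13.9 looks to that comparison to show the benefit of UroLift over invasive surgery.

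**Working it through.** The plan gives no sample size, alpha or event rate for this comparison, so there is no figure to reproduce. The steps below are illustrations, and their assumptions are labelled.

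**1. Arm size.** With the same events per man in both arms, the ratio of totals equals the ratio of arm sizes. The PUL cap is 55. If the surgical arm had 100 men (assumed), the ratio is 100/55 = 1.82 with no difference in risk.

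**2. Symptom splitting in one arm.** Assumptions: 55 men per arm; Poisson counts; 1.0 non-LUTS AE per man; *m* LUTS episodes per man; identical true rates in both arms; each LUTS episode recorded as *k* AEs in PUL and as 1 in surgery. The expected ratio of totals (PUL/surgery) is (1 + mk)/(1 + m). For m = 0.1 and k = 2 this is 1.2/1.1 = 1.09. For m = 0.3 and k = 3 it is 1.9/1.3 = 1.46.

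The false-rejection rate comes from 4,000 simulated trials per setting, using a two-sided 5% exact conditional test of equal Poisson totals. That test is also an assumption, since the plan names none for counts. Each cell shows the simulated ratio, which agrees with the formula to within 0.01, and then the rejection rate.

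| m | k = 1 | k = 2 | k = 3 | k = 7 |
|---|---|---|---|---|
| 0.1 | 1.00; 3.5% | 1.09; 7% | 1.18; 17% | 1.54; 65% |
| 0.3 | 1.00; 4.0% | 1.23; 26% | 1.46; 66% | 2.39; 99% |
| 0.6 | 1.00; 4.6% | 1.38; 59% | 1.76; 96% | 3.25; 100% |

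**3. The same splitting in both arms.** A shared rule removes the bias but not the clustering. With m = 0.3 and splitting in both arms, the same test, which treats events as independent, rejects in 8% (k = 2), 15% (k = 3) and 38% (k = 7) of trials.

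**4. Men with at least one event.** Under the same assumptions this proportion is 1 − exp(−(1 + m)), whatever the value of k: 67% for m = 0.1, 73% for m = 0.3 and 80% for m = 0.6, the same in both arms. Splitting has no effect on it, each man contributes one binary value, and the chi-square and Fisher tests already named in section 16.6 apply.

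**5. Scope, window and cut, side by side.**

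| | PUL | Surgery |
|---|---|---|
| AE scope | All AEs, asked at each visit (14.5) | Selected categories, if in the chart (15.8.2, 15.8.3) |
| AE collection | To 12 months (10.8) | To 12 months (15, 15.8.3) |
| Clavien-Dindo review | Onset within 90 days (14.6) | Not stated in section 15; 14.6 neither names nor excludes surgery |
| Clavien-Dindo cut in item 1 | IIb or above; Table 10 has no IIb | Same |

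**The case against.** **A tempting stronger reading.** A reader might infer that PUL events are graded only to 90 days while surgical events are graded to 12 months, so that the surgical Clavien-Dindo total is inflated. The documents do not support this. AEs are collected to 12 months in both arms. The 90-day limit in section 14.6 runs from the index procedure, which Table 2 defines generically and section 15.3 applies to the surgery. On that wording the limit can cover both arms, and if it does, the contrast vanishes. What can be said is that the surgical grading window is not clearly stated.

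**The independent reviewer may already cover surgery.** Section 14.6 does not restrict the review to PUL, section 14.5 speaks of all enrolled subjects, and section 15.4 uses the same term for retrospective patients, whose data go into the study EDC. The Safety Plan and the written abstraction guidelines mentioned in Table 12 are not in the documents and may settle the grading and counting rules. It is therefore fair to ask for clarification, but not to assert that surgical events go ungraded or are graded differently.

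**Rates are also planned.** Item 2 gives percentages, and sections 1 and 6.4 speak of AE rates. This softens the point. However, item 2 names related AEs only, not SAEs or Clavien-Dindo events, states no denominator, and draws on the same differently built records.

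**The splitting rule is narrow.** Only LUTS are split, and only new or worsened conditions count as AEs. The effect falls mainly on the related-AE total, and there is no clear reason for it to move the SAE or Clavien-Dindo totals much. This stands.

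**Totals can be tested properly.** Count models with exposure and allowance for clustering exist, so a test of totals is not wrong in principle. The plan specifies no such model.

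**This is a feasibility study.** It has no success criteria (section 16.7) and the comparison is declared unpowered. That lowers the weight of the point. It does not make non-comparable totals worth testing.

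**Conclusion.** The point holds in this form: item 1 puts significance statements on event totals that lack a denominator, a common window, a common counting rule and a common AE scope, so the totals can differ for reasons of counting alone.

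The size depends on inputs that the plan does not give. The arm-size effect is 1.82 for an assumed 100 surgical men. The splitting effect is a ratio of 1.09 to 3.25 over the assumed range of m and k, with false rejection from 7% to 100%. The low end (m = 0.1, k = 2) is mild.

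No net direction can be claimed. Splitting and direct questioning raise the PUL total, while a surgical arm larger than PUL would raise the surgical total. The undefined IIb cut has to be resolved in any case. Given the feasibility purpose, this is a change that should be made; it does not threaten the primary assessment.

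**What to change.** Replace item 1 in section 16.6 with the number and percentage of men in each arm who have (a) at least one related AE, (b) at least one SAE and (c) at least one Clavien-Dindo event at a cut that exists in Table 10. Require onset within 90 days of the index procedure in both arms, and compare by Fisher's exact or chi-square test. In addition:

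- Restrict the AE comparison to the categories collected in both arms. Because the unit is the man, several LUTS in one man then count once.
- Show event totals and 12-month figures for each arm descriptively, with denominators and without p-values.
- State that the relatedness, sequelae and grading rules of sections 14.4 and 14.6 apply to both arms.
- State as a limitation that charts may under-record events compared with asking at each visit. The per-man measure does not remove this.

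The cost is SAP wording. If surgical events are not already going to the independent reviewer, applying the same rules will take some extra review time. The downside is that events after day 90 move to a descriptive table.
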